7.6.2 Secondary Efficacy Analysis

7.6.2.1.1 Double-blind treatment phase

1. Mean change in PANSS subscale scores from baseline at Week 6
2. Mean change in PANSS five-factor model scores from baseline at Week 6
3. Mean change in CGI-S score from baseline at Week 6

The secondary variables (1) to (3) will be analyzed using the MMRM method

Statistical Analysis Plan

Version: 2

Study No. D4904020

described above for the primary efficacy variable in the mITT population. This analysis will be repeated by country. Also (3) will be repeated by race as well as country. The secondary variables (1) and (3) will also be analyzed using the LOCF ANCOVA on the mITT population by the method described above for the primary efficacy variable. Additionally, change from last measurement value in the double blind treatment phase for PANSS total score by visit will be summarized for the open-label population. This analysis will be repeated by country.

In addition to analysis described above, the secondary variables (1) to (3) and their change from baseline will be summarized by visit (including LOCF endpoint) and treatment group.

The estimates of the change from baseline in PANSS subscale scores, five factor model scores, and CGI-S score obtained by the MMRM model will be plotted with +/- SE.

Adjusted p-value will not be calculated in any secondary efficacy analysis, even though they use same MMRM method and options as the primary efficacy variable.

4. Proportion of subjects who achieve a response, defined as 20% or greater improvement from baseline in PANSS total score at Week 6

Subjects having a greater or equal to 20% improvement from baseline in PANSS total score at Week 6 (LOCF) will be defined as “responders”. The PANSS total score percentage change will be defined as $[(\text{value at Week 6 (LOCF)} - 30) - (\text{baseline value} - 30)] \times 100 / (\text{baseline value} - 30)$. Subjects having a greater or equal to 30%, 40% and 50% improvement will also be analyzed.

The responder indicator will be set to 1 for responders, set to 0 for non-responder, or set to missing if the percentage is missing. A logistic regression will be performed utilizing the 0-1 responder indicator as the dependent variable, treatment and pooled study center as categorical variables and baseline PANSS total score as a covariate. If the model fails to converge, the model which replace pooled study center to country will be attempted. If still the model failed to converge, the model was attempted with only treatment group and baseline score. If the model ends up not to converge regardless of any attempts described earlier, that should be mentioned in the associated tables.

Estimates for odds ratio and its 95% CI and chi-square p-values will be presented for each DSP-5423P treatment group versus placebo. A similar summary will be presented by country. These analyses will be performed for the mITT population only.

The mock SAS code for logistic regression is given below:

SUMITOMO DAINIPPON PHARMA CO., LTD. CONFIDENTIAL

```
proc logistic data=&ads;
class trt01p site / param=ref;
model responder(event='1')=trt01p site base;
contrast '40MG vs. PLCB' trt01p 1 0 / estimate=exp;
contrast '80MG vs. PLCB' trt01p 0 1 / estimate=exp;
ods output ContrastEstimate = ContrastEstimate;
run; * contrast statement need to be checked by the code list;
```

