### **6.2 Secondary Endpoints**

- Change in PANSS subscale scores from baseline at Week 6
- Change in PANSS five-factor modelNote scores from baseline at Week 6
- Change in Clinical Global Impressions – Severity of Illness (CGI-S) score from baseline at Week 6
- Change in PANSS total score from the last evaluation before the initial application of DSP-5423P at each visit
- Change in PANSS subscales from the last evaluation before the initial application of DSP-5423P at each visit
- Change in PANSS five-factor models from the last evaluation before the initial application of DSP-5423P at each visit
- Proportion of subjects who achieve a response, defined as 20% or greater improvement from baseline in PANSS total score at Week 6

- Change in CGI-S score from the last evaluation before the initial application of DSP-5423P at each visit
- Time to treatment discontinuation from the initial application in the open-label treatment phase

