### **15.3.5.3 Secondary Efficacy Endpoint Analysis**

#### **15.3.5.3.1 Double-blind treatment phase**

1. Change in PANSS subscale scores from baseline at Week 6
2. Change in PANSS five-factor model scores from baseline at Week 6
3. Change in CGI-S score from baseline at Week 6
4. Proportion of subjects who achieve a response, defined as 20% or greater improvement from baseline in PANSS total score at Week 6

The secondary variables (1) to (3) will be analyzed using the MMRM method described above for the primary efficacy variable in the mITT population. The secondary variables (1) and (3) will also be analyzed using the LOCF ANCOVA on the mITT population, by the method described above for the primary efficacy variable. The secondary variable (4) will be analyzed using a logistic regression model, which will include baseline PANSS total score, pooled study center, and treatment.

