### **15.3.8.3 Missing Data**

For the rating scales that consist of more than one item, if any item is missing, then the total and subscale scores will also be handled as missing.

In the efficacy analysis on data collected in the double-blind treatment phase, the primary method for handling of missing data will be the MMRM without explicit imputations for missing data. The LOCF method will be used for an analysis of sensitivity. The final post-baseline data in the double-blind treatment phase will be carried forward and will be defined as the Week 6 (LOCF). The final post-baseline value of the entire study duration will be defined as LOCF endpoint for all subjects.

In the safety analysis, the final post-baseline data in the double-blind treatment phase will be carried forward and will be defined as the Week 6 (LOCF). The final post-baseline value of the entire study duration will be defined as the LOCF endpoint for all subjects.

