6.3 Analysis visits, baseline, and post-baseline measures

All data will be organized and analyzed according to the scheduled timing as outlined in Table 4 to Table 6 Schedule of Assessments and according to the visit denoted in the CRFs. Unscheduled visits may be used if scheduled visits are not available, as specified below. The data collected at the discontinuation visit within 7 days from the final application of study drug will be mapped to the next scheduled visit of the actual discontinuation date, as specified below.

Follow to assign analysis visit;

1. Decide post-base line measures,
2. Assign scheduled visit denoted in the CRFs,
3. Assign CRF discontinuation visits,
4. Assign CRF unscheduled visits, when applicable.

A. Double-blind treatment phase

(i) Baseline analysis visit

Defined as the last non-missing data of CRF Screening or CRF Day 1 (Baseline) visit on or before Day 1. Unscheduled visits will not be used.

Statistical Analysis Plan

Version: 2

Study No. D4904020

(ii) Post-baseline data

Defined as the non-missing data on Day 1 through 7 days after the final application of study drug except for Screening and Day 1 (Baseline) visit. Data assessed on Day 1 and captured in the CRF visits of Week 1, discontinuation, and unscheduled visits will be considered as post-baseline data. Data assessed on Day 1 and captured in the CRF visits of Screening and Day 1 (Baseline) will NOT be considered as post-baseline data.

(iii) Post-baseline analysis visit

The post-baseline data will be mapped to post-baseline analysis visits, ie, Week 1, 2, 4, and 6 as follows:

- (1) CRF Week 1, 2, 4, and 6 will be mapped to the corresponding analysis visits, regardless of the actual day of assessment.
- (2) CRF discontinuation visits will be mapped to the earliest missing analysis visit based on the relative day of assessment as follows:

Assessments and tests	Relative Day	Analysis Visit
PANSS, CGI-S, DIEPSS, C-SSRS, Skin irritation assessment, Body weight, Vital signs	Day 1 to 11	Week 1, 2, 4, 6
	Day 12 to 25	Week 2, 4, 6
	Day 26 to 39	Week 4, 6
	Day 40 or later	Week 6
12-lead ECG, Pharmacokinetic	Day 1 to 11	Week 1, 2, 6
	Day 12 to 25	Week 2, 6
	Day 26 or later	Week 6
Laboratory test	Day 1 to 25	Week 2, 6
	Day 26 or later	Week 6

Note: non-missing analysis visits will not be replaced.

- (3) CRF unscheduled visits will be mapped to the earliest missing analysis visit based on the relative day of assessment as follows:

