6.4 Missing Data

Individual missing item in any scale will not be imputed. For the rating scales that consist of more than one item, if any item is missing, then the total and subscale scores will also be handled as missing. For example, if one item of PANSS positive subscale is missing, then the PANSS total score, the PANSS subscale scores, and the PANSS five-factor model scores will be missing.

In computing LOCF, unscheduled visits in the double-blind treatment phase will be used. For example, for the double-blind treatment phase, Week 6 (LOCF) endpoint will be the last observation of the post-baseline data specified in 6.3 A. Unscheduled visits in the open-label treatment phase will not be used for Week 52 (LOCF) endpoint.

In the efficacy analysis on data collected in the double-blind treatment phase, the primary method for handling of missing data will be the MMRM without explicit imputations for missing data. The LOCF method will be used with analysis of covariance (ANCOVA) as additional sensitivity analysis. The final post-baseline data in the double-blind treatment phase (on or after Day 1 and through 7 days after the date of final application of the study drug for the double-blind treatment phase) will be carried forward and will be defined as the Week 6 (LOCF) endpoint.

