8 CHANGES IN PLANNED ANALYSES

Not applicable.

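### PANSS response is labelled a Week 6 endpoint but scored only on the last observation carried forward, so a subject who stops in Week 1 or 2 can count as a Week 6 responder

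*SAP*

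**What the plan says.** **Protocol.** Section 6.2 lists the endpoint as "Proportion of subjects who achieve a response, defined as 20% or greater improvement from baseline in PANSS total score at Week 6". Section 15.3.5.3.1 repeats the definition and adds: "The secondary variable (4) will be analyzed using a logistic regression model, which will include baseline PANSS total score, pooled study center, and treatment". Neither section says what happens when the Week 6 score is missing. Section 15.3.8.3 makes MMRM the main way of handling missing double-blind efficacy data and says of the alternative: "The LOCF method will be used for an analysis of sensitivity". The same section defines a Week 6 (LOCF) value as the final post-baseline value of the double-blind phase, carried forward.

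**SAP.** Section 3.2 and the title of item 4 in section 7.6.2.1.1 keep the plain Week 6 label. The sentence that defines a responder does not: "Subjects having a greater or equal to 20% improvement from baseline in PANSS total score at Week 6 (LOCF"). The percentage-change formula beneath it also uses the Week 6 (LOCF) value. The 30%, 40% and 50% thresholds are added in the same paragraph with no separate rule. The analysis is confined to the mITT population.

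Section 6.4 states: "Week 6 (LOCF) endpoint will be the last observation of the post-baseline data specified in 6.3 A". Section 6.3 A gives the window for those data: "Defined as the non-missing data on Day 1 through 7 days after the final application of study drug". Section 8, on changes in planned analyses, reads "Not applicable".

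**The concern.** A responder rate at Week 6 is normally read as the share of patients who were better after six weeks. Under the SAP it is the share who were better at their last rating, whenever that was. Someone who improves during the compulsory inpatient stay (to Day 14) and then stops is counted exactly like a completer with a sustained response.

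Response is also treated differently from the other double-blind secondary variables. The PANSS subscales, the five-factor scores and CGI-S are all analysed by MMRM, and LOCF ANCOVA is an additional analysis for the subscales and CGI-S. For response, LOCF is the only analysis, so nothing in the plan shows how far the result depends on it.

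**Working it through.** **1. Can an early stopper be a Week 6 responder?**

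- Entry to the model: a single PANSS total after baseline is enough for mITT (SAP 5.1).
- Value used: the last post-baseline rating, unscheduled visits included, up to 7 days after the last patch (SAP 6.3 A and 6.4). There is no minimum time on treatment. The discontinuation assessment is due within 5 days of the last application (Protocol 13.2), so it falls inside the window.
- Formula (SAP 7.6.2.1.1): [(last value − 30) − (baseline − 30)] × 100 / (baseline − 30).
- Example: baseline 80, the minimum at randomization (Protocol 8.2.1); treatment stopped about Day 8; last score 70. Result: (40 − 50) × 100 / 50 = −20%, which meets the threshold. A baseline of 100 with a last score of 86 gives (56 − 70) × 100 / 70 = −20%, also a responder.

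The SAP sets the indicator to missing only if the percentage is missing. Every mITT subject has a post-baseline total, so this has essentially no cases: each mITT non-completer is classified by the last rating.

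**2. How many subjects could this touch?**

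The documents state no dropout rate. The planned numbers imply one: 133 / (1 − 0.20) = 166.25, rounded up to 167 per group, and 3 × 167 = 501, which reproduces the target. So 167 − 133 = 34 per group, or 34/167 = 20.4%. This is an upper figure for the present purpose, because dropouts with no post-baseline PANSS never enter mITT. SAP Appendix II lists 582 randomized, about 194 per arm; 20% of 194 is about 39 per arm.

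**3. Effect on the responder rates**

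Assume that 10% to 40% of non-completers meet the 20% threshold at their last rating. Their share of each arm's rate is 0.2036 × 0.10 = 2.0 points to 0.2036 × 0.40 = 8.1 points.

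The shift in the active-minus-placebo difference, compared with scoring every non-completer 0 and with equal dropout in each arm, is:

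| Non-completers qualifying, active / placebo (assumed) | Shift |
|---|---|
| 40% / 10% | 0.2036 × 0.30 = +6.1 points |
| 30% / 15% | 0.2036 × 0.15 = +3.1 points |
| 10% / 30% | 0.2036 × (−0.20) = −4.1 points |

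**4. Effect on the odds ratio**

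Illustration, with assumptions not in the documents: 20% dropout per arm and completer response of 35% on placebo and 50% on active.

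- Non-completers scored 0: 0.8 × 0.35 = 28% and 0.8 × 0.50 = 40%; OR = (0.40/0.60) / (0.28/0.72) = 1.71.
- LOCF, 30% of dropouts qualify in both arms: 34% and 46%; OR 1.65.
- LOCF, 30% qualify on active and 10% on placebo: 30% and 46%; OR 1.99.
- LOCF, 10% qualify on active and 30% on placebo: 34% and 42%; OR 1.41.

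**The case against.** The strongest reply is that the SAP breaks no rule. The protocol gives no missing-data method for the logistic model, and its MMRM approach does not apply to that model. Week 6 (LOCF) is a term the protocol itself defines. A reader might infer from the entry in SAP section 8 that the sponsor changed the endpoint without declaring it. The documents do not support that: the SAP specified something left open. What stands is narrower. It filled the gap with the method that the protocol assigns to sensitivity analysis, planned nothing beside it, and kept a label that does not describe it.

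Second, scoring non-completers 0 is also a convention and is nowhere in the protocol. It produces a composite of response and completion, and it penalises the arm with more dropout. With the completer rates above but 30% dropout on placebo and 15% on active, it gives an OR of 2.28, against 1.86 among completers. That is right, and it is a reason to show both versions.

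Third, SAP 6.3 A maps a discontinuation rating to the earliest missing visit. A rating from Day 26 to 39 becomes Week 6 data in the primary MMRM when Week 4 is already filled. A responder rule that ignores it has to say so.

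There is some mitigation. PANSS is rated before other antipsychotics begin (Protocol 11.2.1). Discontinuations are tabulated by arm and reason (SAP 7.2), and retention to 42 days is reported (SAP 7.6.2.1.2). These show who left, but not how many of them were counted as responders.

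**Conclusion.** The concern holds as a mismatch between label and scoring, with no analysis that matches the label. On the SAP's own rules, a subject who stops in Week 1 or 2 with a 20% improvement at the last rating is a Week 6 responder.

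Up to about 2 to 8 percentage points of each arm's rate could come from non-completers. This rests on about 20% non-completion (inferred, and an upper figure) and on 10–40% of them qualifying (assumed).

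It is tempting to go further and say that LOCF favours the drug, on the view that adverse-event dropouts carry forward good scores and lack-of-efficacy dropouts poor ones. Nothing in the documents supports that pattern. The illustrated shifts run from about +6 to −4 points, so the direction cannot be determined.

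The endpoint is secondary and SAP 7.6.2.1.1 calculates no adjusted p-values for it. The primary MMRM and its type I error control are untouched.

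**What to change.** In SAP 7.6.2.1.1:

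- Add a responder analysis for all four thresholds, with the same logistic model and the mITT population. Score 0 for any subject who discontinued double-blind treatment or has no PANSS at the scheduled CRF Week 6 visit.
- State that discontinuation ratings mapped to Week 6 under SAP 6.3 A do not count as Week 6 response in this analysis.
- Use this as the Week 6 responder result. Keep the existing analysis as supportive and label it Week 6 (LOCF).
- Record the clarification in SAP section 8, presented as the sponsor's choice of rule and not as one the protocol already states.

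The cost is one extra derived flag and lower responder rates in every arm, by up to about 8 points under the assumptions above. No new data are needed, and the primary MMRM is unaffected.

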7.6.2.1.2 Time to Treatment Discontinuation

The time to treatment discontinuation for the double-blind treatment phase and the open-label treatment phase will be analyzed using the Kaplan-Meier method for m ITT population or the open-label population respectively. The time to treatment discontinuation will be listed.

- All cause discontinuation will be considered as an event in both the double-blind treatment phase and the open-label treatment phase.
- Subjects who completed the double-blind treatment phase, subjects will be censored at the final application date of the study medication of the double-blind treatment phase.
- Time to treatment discontinuation for the double-blind treatment phase will be determined as the final application date in the double-blind treatment phase – the initial application date in the double-blind treatment phase + 1.
- Subjects who completed the open-label treatment phase, subjects will be censored at the final application date of the study medication of the open-label treatment phase.
- Time to treatment discontinuation for the open-label treatment phase will be determined as the final application date in the open-label treatment phase – the initial application date in the open-label treatment phase + 1.

Kaplan-Meier estimate for 25, 50, and 75 percentiles for time to treatment discontinuation and Kaplan-Meier plots by treatment group will be provided. Additionally, in summary for the double-blind treatment phase, number and percentage of subjects who stay the study for 42 days and its 95%CI will be provided, and in summary for the open-label treatment phase, number and percentage of subjects who

stay the study up to 28 weeks (196 days), and 52 weeks (364 days) and its 95%CI will be provided,

These will be repeated by country. In this case, number and percentage of subjects who stay the study up to 52 weeks (364 days) and its 95%CI will be summarized only for Japan.

The mock SAS code for Kaplan-Meier analysis is given below:

```
proc lifetest data=&ads plots=survival(atrisk);  
strata trt01p;  
time tte*censor(1);  
ods output quartiles=mst;  
run;  
* tte is the variable for time to discontinuation;  
* if completer then censor=1; else censor=0;
```

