#### **13.2 Clinical Assessments after Study Drug Discontinuation**

Every effort should be made for all randomized subjects prematurely discontinuing the study drug, regardless of cause, to undergo final evaluation procedures, in accordance with the discontinuation visit and the follow-up visit as described in Table 4 Schedule of Assessments for outside Japan (p11) or Table 5 Schedule of Assessments for Japan (p13). The subject will undergo the discontinuation assessments within 5 days of the last study drug application. However, if a subject completes the double-blind treatment

phase and discontinues before entering the open-label treatment phase, the subject will undergo the follow-up visit in Table 4 or that in Table 5.

Subjects with study drug application during the washout phase and prematurely discontinuing before randomization, will undergo the following safety assessments: study treatment compliance, skin irritation assessment, laboratory test, 12-lead ECG, body weight, body temperature, blood pressure, pulse rate, and adverse event monitoring at the discontinuation visit in Table 4 Schedule of Assessments for outside Japan (p11) or Table 5 Schedule of Assessments for Japan (p13).

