5.1 Modified intention-to-treat population (mITT population)

The mITT population will consist of all subjects who meet all the following:

- Subjects who are randomized and apply the study drug at least once in the double-blind treatment phase.
- Subjects who have baseline and at least one post-baseline PANSS total score rated in the double-blind treatment phase.

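### The double-blind time-to-discontinuation analysis requires a post-baseline PANSS rating, so treated subjects who stop unrated are left out of it; the effect is small and confined to a descriptive output

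*SAP*

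**What the plan says.** SAP 7.6.2.1.2 states that time to treatment discontinuation "will be analyzed using the Kaplan-Meier method for m ITT population or the open-label population respectively", for the double-blind and open-label phases in that order. The event is broad: "All cause discontinuation will be considered as an event in both the double-blind treatment phase and the open-label treatment phase". Time is the final minus the initial application date plus 1, and completers are censored at their final application. Outputs by treatment group are the 25th, 50th and 75th percentiles, the plots and, for the double-blind phase, the percentage staying 42 days with a 95% CI.

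SAP 5.1 gives mITT two conditions. The first is treatment: "Subjects who are randomized and apply the study drug at least once in the double-blind treatment phase". The second is a rating: "Subjects who have baseline and at least one post-baseline PANSS total score rated in the double-blind treatment phase". Two other sections decide which ratings qualify:

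- SAP 6.3 part A sets the window for post-baseline data: "Defined as the non-missing data on Day 1 through 7 days after the final application of study drug", apart from the Screening and Day 1 (Baseline) visits.
- SAP 6.4 treats the PANSS total as missing when any single item is missing.

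The open-label population (SAP 5.3) has no rating condition. It needs only one application of DSP-5423P in that phase.

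**The concern.** An analysis of all-cause discontinuation should count every treated subject who stops. Here, entry depends on something that happens after randomization and is closely tied to the outcome: staying long enough, or cooperating enough, to be rated. A treated subject who leaves with no qualifying PANSS is almost by definition a discontinuation, and that subject is neither an event nor at risk.

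The rating adds nothing to this analysis. The time variable needs application dates and the censoring flag needs completion status, and neither depends on a PANSS having been done. The open-label half of the same sentence already works this way, and no all-treated version of the double-blind curve is planned.

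What is at stake is the accuracy of the double-blind retention figures by arm. Readers are likely to consult them when judging how much dropout lies behind a primary MMRM that does not impute missing data. The treated subjects missing from the curve are the same ones missing from that model, so the curve cannot show that loss.

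**Working it through.** The plan states no retention figure and no count of unrated subjects, so there is nothing to reproduce. The size below is an illustration on stated assumptions.

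**Who is removed.** The first scheduled post-baseline PANSS is Week 1, window Day 5 to 11 (Protocol Table 3). A subject who stops before then has a rating only if one is done at a discontinuation or unscheduled visit. Those ratings count: "Data assessed on Day 1 and captured in the CRF visits of Week 1, discontinuation, and unscheduled visits will be considered as post-baseline data". The subjects removed are therefore treated subjects with no rating at all, with only incomplete ratings, or whose only rating came more than 7 days after the last patch.

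**Formula.** Let an arm have N treated subjects, d discontinuations and k discontinuers without a qualifying rating.

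- Retention in all treated subjects: (N − d)/N
- Retention in mITT: (N − d)/(N − k)

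With R for true retention and x = k/N, the mITT figure is R/(1 − x). The numerator does not change, so any k above 0 raises reported retention.

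**Assumed x of 1% and 5%, with R of 70% and 80%:**

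- R = 0.70: 0.70/0.99 = 70.7% (+0.7 points); 0.70/0.95 = 73.7% (+3.7)
- R = 0.80: 0.80/0.99 = 80.8% (+0.8); 0.80/0.95 = 84.2% (+4.2)

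SAP Appendix II lists 582 randomized subjects, about 194 per arm, so 1-5% is about 2 to 10 subjects per arm.

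**Cross-check with counts at the planned 167 per arm, k = 2, 6 and 10:**

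- d = 34, the loss implied by 133 of 167 (34/167 = 20.4%): retention is 133/167 = 79.6% in all treated subjects. In mITT it is 133/165 = 80.6%, 133/161 = 82.6% and 133/157 = 84.7%.
- d = 50: retention is 117/167 = 70.1% in all treated subjects. In mITT it is 117/165 = 70.9%, 117/161 = 72.7% and 117/157 = 74.5%.

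This gives an overstatement of about 1 to 5 points, in line with the formula.

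**Between arms.** The direction depends on which arm has more unrated dropouts.

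- Placebo d = 50, k = 8; active d = 34, k = 2. The true difference in discontinuation is 16/167 = 9.6 points. In mITT it is 42/159 − 32/165 = 26.4% − 19.4% = 7.0 points.
- With k reversed (placebo 2, active 8), it is 48/165 − 26/159 = 29.1% − 16.4% = 12.7 points.
- If true retention is equal and x is 1% in one arm and 5% in the other, a difference appears from nothing: 73.7 − 70.7 = 3.0 points at R = 70%, and 84.2 − 80.8 = 3.4 points at R = 80%.

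**Percentiles.** At 70-80% retention only 20-30% of subjects discontinue. The median and 75th percentile would ordinarily not be reached in either population. At 80% the 25th percentile is not reached either. What changes is the early curve and the 42-day percentage.

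**The case against.** The strongest reply is that little depends on this output. Protocol 6.2 and SAP 3.2 list time to discontinuation as an endpoint for the open-label phase only, and Protocol 15.3.5.3.2 plans Kaplan-Meier only there. The double-blind version is a descriptive addition in the SAP, with no treatment comparison described. All of this stands.

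The excluded subjects are also not hidden. SAP 7.2 tabulates double-blind discontinuations with reasons on all randomized subjects. SAP 7.5.1 summarizes double-blind exposure on both mITT and the safety population, in bands that are weekly up to Day 35, using the same date formula as the time variable. Unrated dropouts therefore appear by arm and by time of stopping. This stands too; what is missing for them is the curve and the 42-day CI.

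Third, the excluded group should be small. Subjects are inpatients until Day 14 (Protocol 10.4). Protocol 13.2 says "The subject will undergo the discontinuation assessments within 5 days of the last study drug application", and a PANSS at that visit falls inside the 7-day window. A reader might infer that early dropouts in general are lost, but most should stay in mITT by this route. It does not bring the number to zero, because the commitment is one of effort: "Every effort should be made for all randomized subjects prematurely discontinuing the study drug, regardless of cause, to undergo final evaluation procedures".

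A reader might also infer that switching to another antipsychotic removes a subject. SAP 5.1 and 6.3 contain no such rule; the window is set by date alone. Protocol 11.2.1 also asks for the PANSS before the first post-treatment antipsychotic.

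**Conclusion.** The mismatch is real on the text: an all-cause discontinuation analysis is run in a population that some discontinuers cannot enter. In any arm with such subjects, reported retention is too high, never too low. On the assumption that 1-5% of treated subjects are unrated and all of them discontinued, the excess is about 0.7 to 4.2 points at 70-80% true retention. Both the unrated rate and the retention range are assumptions. If an arm has no unrated dropouts, its figures are correct.

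Three stronger readings are not supported:

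- A reader might infer that the bias favours DSP-5423P. The documents say nothing about unrated dropout by arm, and the working shows the difference can shrink or grow.
- A reader might infer that all the reported percentiles move later. At the assumed retention, only the 25th could move, and only towards the 70% end.
- A reader might infer that the primary efficacy result is compromised. This population choice concerns the Kaplan-Meier output only.

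Low severity: worth correcting because the correction is simple, not because a trial conclusion depends on it.

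**What to change.** In SAP 7.6.2.1.2, for the double-blind phase, replace mITT with all randomized subjects who applied study drug at least once in the double-blind phase, analysed by assigned group, with no PANSS requirement. Apply this to the percentiles, the plots, the 42-day percentage with its CI, and the repeats by country.

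Spelling the population out is safer than citing the safety population. SAP 5.4 refers to application at any time in the study, which could be read to include the washout placebo patches, and Protocol 15.2 analyses safety by treatment actually received.

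The cost is one population flag and no new data. Reported retention becomes slightly less favourable. The number of events should then agree with the treated discontinuations in the disposition table. The percentages may still differ, because that table divides by all randomized subjects and because completing the phase is not the same as staying 42 days (the Visit 6 window opens at Day 40).
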